### **13.3 Data Quality Assurance**

Parion Sciences or its designated representative will conduct a study site visit to verify the qualifications of each investigator, inspect clinical study site facilities, and inform the investigator of responsibilities and procedures for ensuring adequate and correct study documentation.

The investigator is required to prepare and maintain adequate and accurate case histories designed to record all observations and other data pertinent to the study for each study participant. Study data for each randomized subject will be entered into a CRF by study site personnel using a secure, validated web-based electronic data capture (EDC) application. Parion Sciences will have read-only access to site-entered clinical data in the EDC application.

Instances of missing, discrepant, or uninterpretable data will be queried with the investigator for resolution. Any changes to study data will be made to the CRF and documented in an audit trail, which will be maintained within the clinical database.

### **13.4 Monitoring**

Monitoring and auditing procedures developed or approved by Parion Sciences will be followed to comply with GCP guidelines. On-site checking of the CRFs/SAE Forms for completeness and clarity, cross-checking with source documents, and clarification of administrative matters will be performed.

The study will be monitored by Parion Sciences or its designee. Monitoring will be done by personal visits from a representative of Parion Sciences, or designee (study site monitor), who will review the CRFs/SAE Forms and source documents. The study site monitor will ensure that the investigation is conducted according to the protocol design and regulatory requirements.

### **13.5 Electronic Data Capture**

Parion Sciences will provide the study sites with secure access to and training on the EDC application sufficient to permit study site personnel to enter or correct information in the CRFs on the subjects for which they are responsible.

[figure not shown]
A CRF will be completed for each enrolled study subject. It is the investigator's responsibility to ensure the accuracy, completeness, clarity, and timeliness of the data reported in the subject's CRF. Source documentation supporting the CRF data will indicate the subject's participation in the study and will document the dates and details of study procedures, AEs, other observations, and subject status.

The investigator, or designated representative, will complete the CRF as soon as possible after information is collected.

The audit trail entry will show the user's identification information and the date and time of any correction. The investigator will provide formal approval of all the information in the CRFs, including any changes made to the CRFs, to endorse the final submitted data for the subjects for whom the investigator is responsible.

Parion Sciences will retain the CRF data and corresponding audit trails. A copy of the final archival CRF in the form of a CD or other electronic media will be placed in the investigator's study file.

### **13.6 Publications and Clinical Study Report**

#### **13.6.2 Clinical Study Report**

A clinical study report, written in accordance with the ICH E3 Guideline, will be submitted in accordance with local regulations.

Parion Sciences Incorporated

Vertex Pharmaceuticals Incorporated  
Parion Sciences, Inc.

1 GLOSSARY OF ABBREVIATIONS

Abbreviation	Description
AE	Adverse Event
ALT	Alanine Aminotransferase
AST	Aspartate Aminotransferase
ATC	Anatomical Therapeutic Chemical
BMI	Body Mass Index
CI	Confidence Interval
CTCAE	Common Terminology Criteria for Adverse Events
CM	Concomitant Medication
CS	Compound Symmetry
DMC	Data Monitoring Committee
ECG	Electrocardiogram
EU	Europe
FAS	Full Analysis Set
FEF _{25%-75%}	Forced Midexpiratory Flow Rate
FEV ₁	Forced Expiratory Volume in 1 Second
FVC	Forced Vital Capacity
HS	Hypertonic Saline
IDMC	Independent Data Monitoring Committee
K+	Potassium
max	Maximum
MedDRA	Medical Dictionary for Regulatory Activities
min	Minimum
NA	North America
Na+	Sodium

1006696
 Parion Sciences Incorporated
 CLEAN-PCD
 SAP Version 1.0

Abbreviation	Description
PBO	Placebo
PCD	Primary Ciliary Dyskinesia
pp	Percentage Predicted
PT	Preferred Term
QTcF	Corrected QT Interval by Fridericia's Formula
█	██████████
PR	PR Interval, Segment
QOL	Quality of Life
QOL-PCD	PCD Quality of Life Questionnaire
QRS	The Portion of an ECG Comprising the Q, R, and S Waves, Together Representing Ventricular Depolarization
QTc	QT Interval Corrected
QTcF	QT Interval Corrected by Fridericia's Formula
SAE	Serious Adverse Event
SAP	Statistical Analysis Plan
SD	Standard Deviation
SE	Standard Error
SGRQ	St. George's Respiratory Questionnaire
SI	Standard International System of Units
SOC	System Organ Class
SOP	Standard Operating Procedure
TE	Treatment-Emergent
TEAE	Treatment Emergent Adverse Event
TLF	Table, Listing and Figure
ULN	Upper Limit of Normal

1006696
Parion Sciences Incorporated
CLEAN-PCD
SAP Version 1.0

2 PURPOSE

The purpose of this statistical analysis plan (SAP) is to describe the planned statistical analyses of efficacy endpoints and safety endpoints for the final analysis. The SAP clarifies that analysis of Part A and Part B data will be presented separately. [REDACTED]

[REDACTED]

2.1 RESPONSIBILITIES

[REDACTED] will perform the statistical analyses and are responsible for the production and quality control of all tables, figures and listings.

2.2 TIMINGS OF ANALYSES

The primary analysis of safety and efficacy and pharmacokinetics is planned after all subjects complete all three treatment periods for this study or terminate early from any of the treatment periods during the study. Unless otherwise specified, the analysis includes all data collected in the database through the time of the database lock.

Periodic Independent Data Monitoring Committee Meetings (IDMC) have been held to monitor ongoing subject safety. The details of these analyses are specified in the IDMC charter and IDMC SAP. An unblinded team from [REDACTED] which is independent from the study team performed the analyses to maintain the blinding of the study.

1006696
Parion Sciences Incorporated
CLEAN-PCD
SAP Version 1.0

3 STUDY OBJECTIVES

3.1 PART A

3.1.1 Primary Objective

To evaluate the safety and efficacy of treatment with VX-371, administered with and without 4.2% hypertonic saline (HS) in subjects with primary ciliary dyskinesia (PCD) who are ≥ 12 years of age.

3.1.2 Secondary Objective

To evaluate the effect of VX-371, administered with and without 4.2% HS, on quality of life (QOL) in subjects with PCD who are ≥ 12 years of age.

3.2 PART B

3.2.1 Primary Objective

To evaluate the safety and efficacy of treatment with ivacaftor and VX-371, administered with and without 4.2% HS in subjects with PCD who are ≥ 12 years of age.

3.2.2 Secondary Objective

To evaluate the effect of ivacaftor and VX-371, administered with and without 4.2% HS on QOL in subjects with PCD who are ≥ 12 years of age.

3.3 BRIEF DESCRIPTION

[figure not shown]
This is a Phase 2a, 2-part, multicenter, randomized, double-blind, placebo-controlled, incomplete block crossover study in subjects ≥ 12 years of age with PCD. Part A will consist of Treatment Period 1 and Treatment Period 2, separated by a Washout Period. Part B is optional and will consist of Treatment Period 3; subjects will complete Part A before beginning Part B. There will not be a Washout Period between Part A and Part B.

Approximately 150 subjects will be randomized to 1 of 4 treatment sequences in a 2:2:1:1 ratio in Part A, stratifying for percent predicted forced expiratory volume in 1 second (ppFEV1) severity (< 70 or ≥ 70) as described in [Table 1](#). Subjects who enroll in Part B will have oral ivacaftor added to the treatment they were receiving in Treatment Period 2 of Part A, as described in [Table 1](#).

Table 1. Study PS-G202 Treatment Sequences

1006696
 Parion Sciences Incorporated
 CLEAN-PCD
 SAP Version 1.0

Part A

Part B

Sequence	Treatment Period 1	Treatment Period 2	Treatment Period 3	N
1	VX-371 in 4.2% HS	4.2% HS	4.2% HS + ivacaftor	50
2	4.2% HS	VX-371 in 4.2% HS	VX-371 in 4.2% HS + ivacaftor	50
3	VX-371 in 0.17% saline	Placebo (0.17% saline)	Placebo (0.17% saline) + ivacaftor	25
4	Placebo (0.17% saline)	VX-371 in 0.17% saline	VX-371 in 0.17% saline + ivacaftor	25

Part A Study Duration

Excluding the Screening Period, the planned study duration is 113 days from Day 1 to Safety Follow-up Telephone Call, approximately 28 days after the last dose of study drug.

Part A + Part B Study Duration

Excluding the Screening Period, the planned study duration is 141 days from Day 1 to Safety Follow-up Telephone Call, approximately 28 days after the last dose of study drug.

3.4 SUBJECT SELECTION

Protocol V6.0 section 9 specifies the details of eligibility criteria.

3.5 DETERMINATION OF SAMPLE SIZE

[figure not shown]
3.5.1 Part A

The primary efficacy objective of Part A of this study is to evaluate the efficacy of VX-371 with and without HS in subjects ≥ 12 years of age with PCD. For efficacy analysis, the statistical inferences will be based on change from study baseline. The null hypotheses to be tested are that the mean absolute change from study baseline in ppFEV1 after 28 days of treatment is the same for 1) VX-371 in HS versus placebo; 2) VX-371 versus placebo; and 3) VX-371 in HS versus HS alone.

To have a feasible sample size and study duration, a crossover design has been proposed for Part A of this study. Assuming an SD of 7 percentage points, 50 subjects each for Treatment Sequence 1 and Treatment Sequence 2 are needed to have approximately 81% power to detect a 3 percentage point treatment difference in the mean absolute change in ppFEV1 from study baseline, after 28 days of treatment between VX-371 + HS

1006696
Parion Sciences Incorporated
CLEAN-PCD
SAP Version 1.0

and HS alone. Part A of the study will have approximately 87% power to detect a 4-percentage point change from baseline, after 28 days of treatment in ppFEV1 between VX-371 + HS and placebo. The power to detect a 3 percentage point difference between VX-371 and placebo is about 51%. The sample size estimate was based on 10000 simulation runs with an incomplete block design assuming no dropouts. In the simulation, the correlation between responses to the 2 treatments within a subject was assumed to be 0. Furthermore, a 2-sided significance level of 0.05 was used in the sample size determination with no multiplicity adjustment. The sample size also takes into consideration an assumed dropout rate of 10%.

Part A of the study will enroll approximately 150 subjects. However, as no therapeutic intervention study has previously been completed in PCD patients, the ability to enroll all 150 subjects is uncertain. Enrollment of less than 150 subjects will still provide useful information and could demonstrate an important difference between treatments. Enrollment into Part A will continue until approximately 150 subjects are randomized or the enrollment rate drops, despite suitable interventions, such that the planned enrollment cannot be achieved.

3.5.2 Part B

No formal sample size calculation was performed. All subjects who completed the assigned treatment in Part A and who meet the eligibility criteria for Part B will be offered enrollment in Part B.

3.6 TREATMENT ASSIGNMENT & BLINDING

[figure not shown]
Approximately 150 subjects will be randomized to 1 of 4 treatment sequences in double-blind fashion when they are determined to have met all eligibility criteria. Subjects will be randomized in a 2:2:1:1 ratio, in Part A to one of the 4 treatment sequences, (Treatment Sequence 1 or Treatment Sequence 2; Treatment Sequence 3 or Treatment Sequence 4), stratifying for ppFEV1 severity (<70 or ≥70). Randomization must only occur after all inclusion and exclusion criteria are met and before the first dose of inhaled study drug is administered in Part A on Day 1.

An interactive web or voice response system (IXRS) will be used to assign subjects to treatment based a centralized randomization scheme. The randomization code will be produced by [REDACTED]. The Parion Sciences study biostatistician, or designee, will review and approve the dummy randomization list. The final randomization list will be reviewed and approved by a designated unblinded [REDACTED] biostatistician responsible for the IDMC analyses to maintain the study blind throughout the course of the study until the final database lock.

There is no randomization in Part B. Subjects will remain in the same treatment as in

1006696
Parion Sciences Incorporated
CLEAN-PCD
SAP Version 1.0

[figure not shown]
Treatment Period 2 of Part A and will also receive open-label oral ivacaftor.

3.7 ADMINISTRATION OF STUDY MEDICATION

Protocol V6.0 section 10 specifies the details of study drug administration.

3.8 STUDY PROCEDURES AND FLOWCHART

A schematic of the study design is provided below:

This study includes the following:

1. **Screening Period:** Day of Screening Visit until Day 1 (first dose of study drug). The Screening Visit can occur Day -38 to Day -5, relative to the first dose of study drug

2. Treatment Periods:

Part A:

- Treatment Period 1: Day 1 (first dose of study drug) through Day 29 (28 days of treatment)
- Washout Period: Day 29 through Day 56 (28 days)
- Treatment Period 2: Day 57 through Day 85 (28 days of treatment)

1006696
Parion Sciences Incorporated
CLEAN-PCD
SAP Version 1.0

Part B (Optional):

- Treatment Period 3: Day 85 (first dose of oral ivacaftor) through Day 113 (28 days of treatment)
3. **Safety Follow-up Period:** 28 days (\pm 7 days) after the last dose of study drug.

If the subject prematurely discontinues study drug, an Early Termination of Treatment (ETT) Visit should be scheduled as soon as possible after the subject decides to terminate study drug treatment. Subjects who prematurely discontinue treatment will also be required to complete the Safety Follow-up Telephone Call approximately 28 days (\pm 7 days) after their last dose of study drug.

If the subject meets the criteria for study participation and is taking HS at the time of Screening, the subject will be instructed to stop their usual regimen of inhaled HS for the duration of the study, beginning at least 28 days before the first dose of study drug in the study and continued through completion of the last study visit. If a subject is not taking HS as part of their ongoing PCD treatment, the Day 1 Visit may be scheduled to occur as soon as 5 days after the Screening Visit, provided that results of all screening procedures have been received. Each subject will be instructed to use an appropriate airway clearance technique throughout the study.

Schedules of Assessments are shown in [Appendix IV Table 5](#), [Table 6](#) and [Table 7](#)

1006696
Parion Sciences Incorporated
CLEAN-PCD
SAP Version 1.0

4 ENDPOINTS

[figure not shown]
4.1 PART A

4.1.1 Primary Endpoints

- Results of safety and tolerability assessments of adverse events (AEs), clinical laboratory values (urine, serum and plasma chemistry, and hematology), 12-lead electrocardiograms (ECGs), spirometry, vital signs, and pulse oximetry
- Absolute change in ppFEV1 from study baseline, after 28 days of treatment in Part A

4.1.2 Secondary Endpoints

- Change in QOL score as measured by the Quality of Life-PCD Questionnaire (QOL-PCD) and the St. George's Respiratory Questionnaire (SGRQ)^[1] from study baseline, after 28 days of treatment in Part A

4.2 PART B

4.2.1 Primary Endpoints

- Results of safety and tolerability assessments of AEs, clinical laboratory values (urine, serum and plasma chemistry, and hematology), 12-lead ECGs, spirometry, vital signs, and pulse oximetry

[figure not shown]
1006696
Parion Sciences Incorporated
CLEAN-PCD
SAP Version 1.0

- Absolute change in ppFEV1, from study baseline and Part B baseline after 28 days of treatment in Part B

4.2.2 Secondary Endpoints

- Change in QOL score as measured by the QOL-PCD and SGRQ from study baseline and Part B baseline, after 28 days of treatment in Part B

1006696
Parion Sciences Incorporated
CLEAN-PCD
SAP Version 1.0

5 ANALYSIS SETS

5.1 SCREENED SUBJECTS

Screened subject for Part A is defined as any subject who signed the study specific informed consent and had at least one study procedure performed during the screening period.

5.2 ALL SUBJECTS SET

5.2.1 Part A

The Part A All Subjects Set is defined as all subjects who were randomized or received at least 1 dose of study drug in Part A. Part A subject data listings will be referenced using the Part A All Subjects Set, unless otherwise specified.

5.2.2 Part B

The Part B All Subjects Set is defined as all subjects who enrolled (signed the Part B informed consent) in Part B.

5.3 FULL ANALYSIS SET

5.3.1 Part A

The Part A Full Analysis Set (FAS) is defined as all randomized subjects who received at least 1 dose of study drug in Part A and had a confirmed diagnosis of PCD. The Part A FAS subjects will be analyzed according to the treatment to which they were assigned in each period of Part A. Data for a period will be used provided that the subject received at least 1 dose of study drug in that Treatment Period.

5.3.2 Part B

The Part B FAS is defined as all subjects who had a confirmed diagnosis of PCD and received at least 1 dose of ivacaftor in Part B. The Part B FAS subjects will be analyzed according to the treatment as enrolled in Part B, which is ivacaftor plus the same treatment as assigned in Part A Treatment Period 2.

1006696
Parion Sciences Incorporated
CLEAN-PCD
SAP Version 1.0

5.4 SAFETY SET

5.4.1 Part A

The Part A Safety Set is defined as all subjects who received at least 1 dose of study drug in Part A. The Part A Safety Set subjects will be analyzed according to the treatment they received in each period of Part A. Data for a period will be used provided that the subject received at least 1 dose of study drug in that Treatment Period.

5.4.2 Part B

The Part B Safety Set is defined as all subjects who received at least 1 dose of ivacaftor in Part B. The Part B Safety Set subjects will be analyzed according to the treatment they actually received in Part B.

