### 8.1.3.2 Part B

Part B comprises Treatment Period 3 and is optional.

#### 8.1.3.2.1 Treatment Period 3

In order to continue into Treatment Period 3 the subject must sign the Part B informed consent form (ICF) or assent, as applicable. The ICF should be signed before the Day 85 Visit to allow for delivery of study drug for Treatment Period 3.

Study visits will occur on Day 85 (also the last visit of Treatment Period 2) and Day 113 to allow for a full 28 days of study drug (inhaled study drug and oral ivacaftor).

On Day 86 and Day 87, until the telephone call is no longer required by the IDMC, subjects will have a telephone call for safety purposes (e.g., inquire about AEs). If necessary, the subject may be asked to return to clinic to follow up on a new medical problem.

The first dose of both ivacaftor and inhaled study drug in Treatment Period 3 will be administered at the Day 85 Visit, after completion of the Day 85 pre-dose assessments.

If the first dose of study drug (inhaled study drug and oral ivacaftor) administered in the clinic on Day 85 is taken in the morning, the second dose will be taken that evening. The last home dose of the twice daily study regimen in Treatment Period 3 will be taken on the evening of Day 112 and no dose will be taken on Day 113.

If the first dose of study drug (inhaled study drug and oral ivacaftor) administered in the clinic on Day 85 is taken in the afternoon, a second dose will not be taken that evening. The last home dose of the twice daily study regimen in Treatment Period 3 will be taken on the morning of Day 113, at least 4 hours before the Day 113 Visit.

Subjects should only take study drug at a maximum of twice daily.

Subjects will remain in the clinic for a total of 2 to 4 hours after dosing with study drug at the Day 85 Visit until the IDMC provides approval to only require subjects to remain in clinic for 1 hour post-dosing. The duration (2 to 4 hours) each subject stays in clinic for observation will be left to the discretion of the investigator. If the IDMC does not approve reducing the observation period to 1 hour post-dosing, then subjects will continue to be observed in clinic for 2 to 4 hours during the Day 85 Visit.

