## **Part B**

The Part B FAS is defined as all subjects randomized in Part A and enrolled in Part B and who have received at least 1 dose of study drug in Part B. The Part B FAS is to be used in Part B efficacy analyses in which subjects will be analyzed according to the treatment as enrolled in Part B, which is ivacaftor plus the same treatment as assigned in Part A Treatment Period 2. All analyses of background data and efficacy data in Part B will be based on the Part B FAS.

The Part B Safety Set is defined as all subjects who received at least 1 dose of study drug in Part B. The Part B Safety Set is to be used for all Part B safety analyses in which subjects will be analyzed according to the treatment as enrolled in Part B, which is ivacaftor plus the same treatment as assigned in Part A Treatment Period 2.

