For Part B, 2 types of baseline will be defined. The study baseline is defined as the most recent nonmissing measurement (scheduled or unscheduled) collected before the first dose of study drug (i.e., same baseline as for Part A). The Part B baseline is defined as the most recent nonmissing measurement (scheduled or unscheduled) collected before the first dose of study drug in Part B.

**Change/Absolute Change from Study Baseline in Part A and Part B** will be calculated as:  
post-baseline value - study baseline value

**Change/Absolute Change from Period Baseline in Part A and Part B** will be calculated as:  
post-baseline value - period baseline value

**Change/Absolute Change from Part B Baseline** will be calculated as:  
post-baseline value - Part B baseline value

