6.2 KEY DEFINITIONS

6.2.1 Baseline

Two types of baseline will be defined for Part A. The **study baseline** is defined as the most recent nonmissing measurement (scheduled or unscheduled) collected before the first dose of study drug in the study. The definition will be applied to all demographics, background, and baseline characteristics and efficacy data analyses, including the primary endpoint analysis. The **period baseline** is defined as the most recent nonmissing measurement (scheduled or unscheduled) collected before the first dose of study drug in each Treatment Period. For Part A Treatment Period 2, the period

1006696
Parion Sciences Incorporated
CLEAN-PCD
SAP Version 1.0

baseline will be the first assessment measured after treatment-emergent (TE) period for Period 1. This definition will be applied to all safety data analyses.

For spirometry analysis in Part A, if Period 1 day 1 pre-dose data is not available, data collected at the screening visit before the test HS dose will be used as Period 1 baseline or study baseline instead of the last non-missing screening visit after the test HS dose.

For weight, height and BMI, study baseline and Period 1 baseline will be defined as the most recent non-missing measurement (scheduled or unscheduled) collected before or on the day of the first dose of study drug in Part A, Period 1. Similarly, Period 2 baseline will consider the most recent non-missing measurement (scheduled or unscheduled) collected after the TE period for Period 1 and before or on the day of first dose of study drug in Part A, Period 2.

For SGRQ and QOL-PCD, study baseline will be defined as the most recent non-missing measurement (scheduled or unscheduled) collected before or on the day of the first dose of study drug in Part A, Period 1.

For Part B, two types of baseline, study baseline and Part B baseline, will be defined. The study baseline is defined the same as study baseline for Part A. The Part B baseline is defined as the most recent non-missing measurement (scheduled or unscheduled) collected before the first dose of ivacaftor in Part B and after the last dose in Period 2.

- Change/Absolute change from study baseline in Part A and Part B will be calculated as:

post-baseline value - study baseline value.

- Change/Absolute change from period baseline in Part A will be calculated as:

post-baseline value - period baseline value.

- Change/Absolute change from Part B Baseline will be calculated as:

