6.2.2 Treatment Emergent Period

Treatment-emergent (TE) period for Part A Treatment Period 1:

1006696
Parion Sciences Incorporated
CLEAN-PCD
SAP Version 1.0

- The Treatment-Emergent Period will correspond to the interval from the first dose date of Treatment Period 1 to 28 days after the last dose date of Treatment Period 1 or the date before the first dose date of Treatment Period 2 or the safety follow-up visit, whichever occurs earlier.

TE period for Part A Treatment Period 2:

- The treatment emergent period will correspond to the interval from the first dose date of Treatment Period 2 to 28 days after the last dose date of Treatment Period 2 or the date before the first dose date of Part B or the safety follow-up visit, whichever occurs earlier.

Treatment-Emergent Period for Part B:

- The treatment emergent period will correspond to the interval from the first dose date of study drug in Part B to 28 days after the last dose date of Part B or the safety follow-up visit, whichever occurs earlier.

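### The SAP ties the Part B Safety Set and baseline to ivacaftor but opens Part B treatment-emergence at any study drug, leaving a small gap in the by-treatment safety tables

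*SAP*

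**What the plan says.** **Safety Set.** Protocol section 12.2: "The Part B Safety Set is defined as all subjects who received at least 1 dose of study drug in Part B". SAP section 5.4.2: "The Part B Safety Set is defined as all subjects who received at least 1 dose of ivacaftor in Part B". Protocol section 5.4 explains that study drug, used without a qualifier, covers the inhaled products and oral ivacaftor. I found no different definition in the SAP.

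**Treatment-emergent periods.** SAP section 6.2.2 runs the Part B period "from the first dose date of study drug in Part B to 28 days after the last dose date of Part B", or to safety follow-up if that is earlier. The Period 2 period ends 28 days after the last Period 2 dose "or the date before the first dose date of Part B or the safety follow-up visit, whichever occurs earlier". This second boundary names no drug.

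**Baseline.** Protocol section 12.3.1 takes the most recent Part B baseline value "collected before the first dose of study drug in Part B". SAP section 6.2.1 takes the most recent value, scheduled or unscheduled, "collected before the first dose of ivacaftor in Part B and after the last dose in Period 2".

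**Dosing.** Protocol section 8.1.3.2.1: "The first dose of both ivacaftor and inhaled study drug in Treatment Period 3 will be administered at the Day 85 Visit".

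**Reporting.** SAP section 10 bases Part B safety analyses on the Part B Safety Set. Section 10.1 restricts adverse event tables to treatment-emergent events but lists all adverse events, with a separate listing of deaths and other serious events. SAP section 11, on changes from the protocol, reads as not applicable.

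**The concern.** The protocol uses one trigger throughout, so a subject enters the Part B Safety Set when the Part B treatment-emergent clock starts. The SAP moved the set and the baseline to ivacaftor and left the clock on study drug. A subject who inhales on Day 85 and takes no tablet, for example after a reaction to the inhaled dose, can then leave Part A reporting without entering Part B reporting.

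Safety is a primary endpoint of both parts. Whether a subject falls into the gap can depend on what happened at the Day 85 dosing, so the omission need not be random. The laboratory, ECG, vital sign, spirometry and oximetry summaries for Part B use the same set and share the gap. The Part B Full Analysis Set in SAP 5.3.2 also requires ivacaftor, so Part B disposition would not show the subject either.

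The baseline wording raises a second, smaller issue for a different subject, one who does take the tablet. An unscheduled reading after the inhaled dose and before ivacaftor would displace the Day 85 pre-dose value. Recovery from an acute fall would then count towards the change from Part B baseline, which for ppFEV1 is a Part B primary endpoint.

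**Working it through.** No stated sample size or power figure enters this point. The check applies the SAP definitions to a test subject.

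**Inputs.** Last Period 2 dose on Day 84 (the morning-dosing schedule in Protocol 8.1.3.1.3); first Part B inhaled dose on Day 85; no ivacaftor; safety follow-up 28 days after the last dose.

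**Literal reading of SAP 6.2.2.**
- Period 2 ends at the earlier of Day 84 + 28 = Day 112 and Day 85 − 1 = Day 84, hence Day 84.
- With one inhaled dose, Part B runs from Day 85 to Day 85 + 28 = Day 113, which is 113 − 85 + 1 = 29 days.
- With inhaled drug to Day 112, Part B runs from Day 85 to Day 112 + 28 = Day 140, which is 140 − 85 + 1 = 56 days.
- The subject is outside the Part B Safety Set, so none of these days feeds a by-treatment table. Because the boundary is a date, events on Day 85 before the inhaled dose are included in the gap.

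**Alternative reading: the Period 2 boundary means first ivacaftor.** The subject never reaches it, so Period 2 runs to Day 112 and covers Days 85 to 112, which is 28 days. This assumes that Part B inhaled doses are not counted as Period 2 doses.

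| Case | Literal SAP | Period 2 boundary read as ivacaftor | Protocol Safety Set rule, SAP periods unchanged |
|---|---|---|---|
| One inhaled dose, Day 85 | 0 of 29 days covered | 28 of 29 | 29 of 29 |
| Inhaled drug Days 85 to 112 | 0 of 56 | 28 of 56 | 56 of 56 |

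**Weight of one subject.** The planned size of a 0.17% saline sequence is 25, so one subject is 1/25 = 4 percentage points of a full arm; in a 4.2% HS sequence it is 1/50 = 2 points. Part B is optional, so actual arms may be smaller. The number of affected subjects is not in the documents. Assuming 0 to 3 among at most 150 entrants gives 0/150 = 0% to 3/150 = 2%.

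**Baseline.** Change is the post-baseline value minus the Part B baseline, so a baseline lower by d points raises that subject's change by d. As an illustration only, d = 15 in one of 25 subjects moves the unadjusted arm mean by 15/25 = 0.6 points.

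**The case against.** The strongest reply is that Part B is an ivacaftor add-on. The inhaled treatment carries over from Period 2 without washout, and both documents describe the start of Treatment Period 3 on Day 85 by the first ivacaftor dose. Requiring ivacaftor for its safety set is therefore defensible, and the Period 2 boundary, which names no drug, can be read the same way. This stands in part. The alternative reading closes most of the gap after a single inhaled dose but only half of it if inhaled drug continues. It also conflicts with the Part B boundary in the same SAP section, which says study drug.

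A reader might infer that the affected subject's events vanish from the report. The documents do not support that. SAP 6.1 and 10.1 keep them in listings, including the listing of deaths and serious events. Events with missing or partial start dates can be placed in Part A under SAP 10.1 and Appendix V.

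A reader might also take inability to swallow tablets as a route into the gap. Protocol 9.2.1 bars such subjects from Part B, so that route requires an eligibility deviation. Nor does the row order in Protocol Table 3-2 establish that the inhaled dose comes first; I found no text that fixes the order.

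Finally, restoring the protocol's rule puts a subject who took no ivacaftor into a set whose four treatments all include it, while SAP 5.4.2 analyses by treatment actually received. That is a real drawback, and the fix has to handle it.

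**Conclusion.** The mismatch is real and undeclared; its likely effect is small. Read literally, the SAP leaves a subject with a Day 85 inhaled dose and no ivacaftor out of the by-treatment safety summaries from Day 85 on, for adverse events with known start dates and for the other Part B safety data. Under the ivacaftor reading of the Period 2 boundary, only 1 of 29 or 28 of 56 days stay uncovered. These counts rest on the morning schedule and on follow-up at 28 days.

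The claim that every later event is necessarily missing from every table goes too far, because one boundary is ambiguous and the date rules rescue some events. Cases may be zero. The baseline issue is secondary: it needs an unscheduled reading between two doses at one visit. Part A inference on efficacy is unaffected. Severity: minor.

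**What to change.** - **SAP 5.4.2:** admit anyone with one or more Part B doses of either product, inhaled study drug or ivacaftor, as the protocol does. Footnote or show separately any subject who took no ivacaftor.
- **SAP 6.2.1:** take the Part B baseline before the first Part B dose of any study drug.
- **SAP 6.2.2:** state that the first Part B dose date means the first dose of any study drug, for both the Period 2 and the Part B boundary.
- **SAP 5.3.2:** the Part B Full Analysis Set may keep its ivacaftor requirement.
- **SAP 11:** record every departure from the protocol that is kept, including that one.

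The cost is a few phrases and one footnote or separate row, with no new data. Tying both treatment-emergent boundaries to ivacaftor instead would make the SAP's Part B definitions consistent with each other. It would still leave 28 of 56 days uncovered for a subject who continues inhaled drug without ivacaftor, and it would have to be declared in section 11.
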